15.2.6 Efficacy evaluations

Primary Efficacy Outcome

The primary efficacy outcome will be the percent reduction (change) from baseline in the number of apnea episodes (each ≥ 10 seconds in duration) per hour, during awake time. This will be calculated from the data obtained during home respiratory monitoring by means of an ambulatory data acquisition system (BioRadio™) designed to record specific respiratory and cardiac parameters. Assessment of the respiratory outcomes will be performed at home on any 3 days in each of the first 3 weeks of the Screening period, and in the week prior to each of the visits at Weeks 2, 8, 16, and 24. Monitoring will be performed when the patient is awake and should be attempted for 6 hours on each of the 3 days. Data from all of the quality recording time (minimally 3 hours) in the Screening period, and from the week prior to each of the visits at Weeks 2, 8, 16, and 24, will be averaged and used in calculating the value for the primary efficacy measure. If the patient meets the criterion for number of apnea episodes, as determined by Vivonoetics, in any week of the Screening period, home monitoring in the subsequent week(s) would not be required, and the screening data would be used to calculate the baseline value for the analyses.

The primary efficacy analysis for the initial, 24-week, double-blind, treatment period will be performed on the Intent-to-Treat (ITT) population, consisting of all patients who were randomized to treatment. The percent reduction (change) from baseline in the number of apnea episodes (each ≥ 10 seconds in duration) per hour will be compared between treatment groups using a Mixed Model Repeated Measures (MMRM) analysis. The MMRM model will include percent change from baseline as response, the fixed, categorical effects of treatment group, visit, treatment group-by-visit interaction, and the continuous terms age and baseline value as covariate. A statistically significant difference between high dose sarizotan (5 or 10 mg *bid*) and placebo will be considered evidence of efficacy in reducing apnea.

Key Secondary Efficacy Outcome

The mean rating of the caregiver-rated CIC at Week 24/endpoint will be compared between treatment groups using the Van Elteren test (a stratified Cochran Mantel Haenszel test with modified ridit scores). The following age strata will be considered in the analysis: <13 years and \geq 13 years. In addition to the above analysis, comparisons between treatments for the proportion of patients rated improved at Week 24 will be done using logistic regression.

Other Secondary Efficacy Outcomes

The analysis of the Caregiver Top 3 Concerns will be performed first, comparing the change from baseline in the total score on the VAS for each of the 3 symptoms identified as most concerning at baseline using an ANCOVA-LOCF analysis. The model will include treatment group and the baseline value along with age as covariates. Change will be estimated using the least-squares mean derived from the ANCOVA. Comparisons between treatment groups at Week 24 will be made using the difference in least-squares mean, 95% confidence interval (CI) and p-values from the ANCOVA model.

Descriptive statistics will be presented for the other secondary efficacy outcomes. The proportion of patients rated improved, as well as the mean score, on the Investigator-rated CGI-C at each of the scheduled visits will be presented. Actual values and the change from baseline in other secondary efficacy variables (Motor Behavioral Assessment Scale and subscales, other respiratory parameters, and RCSS) at all scheduled visits will be presented. An additional analysis of efficacy will be performed for patients with a sarizotan plasma concentration of >400 ng/mL.

Multiple Comparisons/ Multiplicity

The study level error rate will be controlled by following a sequential multiple testing procedure, where testing will begin with the primary efficacy endpoint. The effects of the high dose sarizotan versus placebo will be analyzed first for all parameters in a pre-specified sequence.

The sequence of testing will be as presented below:

- Percentage change from baseline in the number of apnea episodes,
- Mean rating of CIC,
- Mean change from baseline in the Top Three Concerns Total Score.

Initial 24-week Double-blind Treatment Period

The primary efficacy assessment for the study will be performed using data from the initial 24-week double-blind, placebo-controlled treatment period. A statistical “Win” will be claimed if the following results are obtained in the primary and key secondary efficacy analyses:

- Statistically significant difference between high dose sarizotan (5 or 10 mg *bid*) and placebo in the percent reduction (change) from baseline in the number of apnea episodes (each \geq 10 seconds in duration) per hour, during awake time;
- Directional change on the CIC in favor of high dose sarizotan (5 or 10 mg *bid*) group compared to placebo.

168-week Open-label Extension Treatment Period

Efficacy data from the extension period obtained from patients randomized to sarizotan at Baseline will be analyzed to determine if there is any attenuation of the benefit noted during the first six months. The response in placebo patients switched to sarizotan in the extension period will be compared with that in patients who were treated with sarizotan throughout the study. Data for the primary and secondary

Amend. 1, 19Jan2016; Amend. 2, 18May2016; Amend. 3, 21Oct2016; Amend. 4, 03Mar2017; Amend. 5, 29Mar2017; Amend. 6, 13Apr2017; Amend. 7, 02Oct2017; Amend. 8, 02Nov2017; Amend. 9, 11Feb2018; Amend. 10, 29Nov2018; Amend. 13, 10Dec2019; Amendment 14, 17 March 2020, Clean, Final

respiratory parameters will be derived from data collected in the clinic using the SOMNOtouch. The statistical methodology to be used in the analyses conducted for the open-label extension treatment period will be described in detail in the Statistical Analysis Plan.

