The 168-week extension treatment period of the study uses an open-label design, such that the Investigator, site staff, caregiver/patient and Sponsor will know what treatment the patient is receiving. To ease the burden on the patient/caregiver, the number of assessments has been reduced in this open-label extension period; in particular in-home cardio-respiratory monitoring using the BioRadio will not be performed. All patients treated in the initial double-blind period, including those randomized to placebo, will have an opportunity to receive open-label treatment with sarizotan for up to 24 weeks in the initial open-label period. Only those patients who are judged by the Investigator to be benefitting from sarizotan treatment, and not experiencing significant adverse events, will be eligible to continue open-label treatment for an additional 144 weeks. The open-label design allows simplification of the packaging, dispensing and dosing of the

study medication. All patients enrolled in the extension period, including those originally randomized to placebo, will receive treatment with sarizotan, and will start at a dose of 2 mg *bid* (patients 4 to <13 years of age and weighing 10 to <18 kg, and patients \geq 13 years of age but weighing <25 kg) or 5 mg *bid* (patients \geq 13 years of age and weighing \geq 25 kg). At Week 28, patients will return to the clinic for safety and efficacy assessments, and will have their dose maintained at 2 mg *bid* (patients 4 to <13 years of age and weighing 10 to <18 kg), increased to 5 mg *bid* (patients 4 to <13 years of age and weighing \geq 18 kg, and patients \geq 13 years of age and weighing <25 kg) or increased to 10 mg *bid* (patients \geq 13 years of age and weighing \geq 25 kg), if the starting dose was well tolerated. Since patients may be receiving sarizotan for the first time or receiving a different dose than in the initial double-blind period, the Week 24 evaluations will be used as the baseline assessments for evaluating changes in the safety and efficacy parameters measured in the extension period.

Sarizotan has not been administered previously to pediatric patients, or patients with RTT; therefore, safety data from all patients will be evaluated periodically by a Safety Monitoring Board (SMB) throughout the study.

Rationale for pharmacokinetic sampling times

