- ^C Safety follow-up to be performed 14 days after the final dose of study medication in the extension treatment period, or if the patient discontinues prematurely.
- ^D Recording of dosing for the final dosing period.
- ^E Patients will be contacted 30 days after their final dose of study medication to follow up on the occurrence of any SAEs.
- ^F Patients will undergo cardiorespiratory monitoring in the clinic at each scheduled visit using a specialized data acquisition system (SOMNOtouch).
- ^G Telephone contact with patient/caregiver will be done on Days 175 and 203 (± 1 day), and at Weeks 54, 66, 78, 90, 102, 114, 126, 138, 150, 162, 174 and 186 (± 1 week), to assess tolerability of the current dose of study medication; adverse events and concomitant medication use will be assessed.
- ^H Patients completing 336 days (± 14 days) of treatment will be considered to have completed the initial 24-week extension treatment period of the study.
- ^I On Day 168 (first dose at 5 mg bid) and Day 196 (first dose at 10 mg bid), vital signs, ECG and physical/neurological examinations will be performed pre-dose and 1 and 4 hr post-dose. At Baseline (Day 168), assessments performed as part of the final Week 24 evaluations in the preceding double-blind period of the study will serve as the pre-dose assessment.
- ^J To be performed for all post-pubertal females.
- ^K Ratings of the CGI-C and CIC for the open-label extension period should be based on the patient's condition at the Week 24 visit.
- ^L The first dose (5 mg) at the starting dose (5 mg *bid*) on Day 168 (Week 24) and the first dose (10 mg) at the target dose (10 mg *bid*) on Day 196 (Week 28) will be administered in the clinic at least 6 hours after the previous dose.
- ^M Informed consent must be obtained at Week 48, at Week 96, and again at Week 144, for the patient to continue open-label treatment for an additional 48 weeks. If in the Investigator's opinion, the patient is benefitting from treatment with sarizotan and is not experiencing any significant adverse events, they will be eligible to continue open-label treatment.
- ^N All Week 96 (Final) evaluations should be performed for subjects who complete Part 1 of the additional open-label treatment period and do not continue open-label treatment, or when a subject discontinues from the study prematurely after Week 48 and prior to Week 96.

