During home monitoring of respiratory function, caregivers should keep a diary and be instructed to record any problems that are encountered with the patient during the monitoring session, e.g., the patient is overly active or falls asleep, the RIP bands become loose or fall off, or the pulse oximeter becomes loose or falls off. The date and starting time of onset for these problems should be noted. The time at which the problem resolves should also be noted. The diary should be brought to the hospital/clinic at each scheduled visit, and the information from the diary will be used in the analysis of the BioRadio data.

Additional assessments of the respiratory outcomes will be performed at the hospital at Baseline and at the Week 16 and 24 visits, using the SOMNOtouch™ (SOMNOmedics GmbH, Randersacker, Germany), a stretch-sensitive resistance plethysmograph device similar to the BioRadio. A period of approximately 1 hour of cardiorespiratory monitoring using the SOMNOtouch will be performed at each of these visits. Data collected using the SOMNOtouch will be analysed and summarized by an external vendor, Vivonoetics.

During the open-label extension phase of the study, patients will return for visits every 4, 8 or 12 weeks, and respiratory assessments will be performed in the clinic using the SOMNOtouch at Weeks 28, 32, 40, 48, 60, 72, 84, 96, 108, 120, 132, 144, 156, 168, 180 and 192 (or at early discontinuation). Respiratory parameters derived from the SOMNOtouch data will be similar to those from the BioRadio, including apnea episodes. Efficacy data from the extension period from patients randomized to sarizotan at Baseline will be analysed to determine if there is any attenuation of the benefit noted during the first six months. In addition, a comparison will be made between patients who received sarizotan throughout both periods of the study

and those who were randomized to placebo in the double-blind period and switched to sarizotan in the open-label extension period.

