15.2 Statistical methods

This is a prospective, 24-week, randomized, double-blind, placebo-controlled study, with a 168-week open-label extension, designed to evaluate the safety, tolerability, and efficacy of two oral doses of sarizotan in patients with RTT with respiratory abnormalities. At least 129 patients will be randomized (approximately 43/group) to receive 24 weeks of double-blind treatment with either low dose sarizotan [sarizotan 2 mg *bid* (age 4 to <13 years; or age \geq 13 years, weight <25 kg) or 5 mg *bid* (age \geq 13 years, weight \geq 25 kg)], high dose sarizotan [sarizotan 5 mg *bid* (age 4 to <13 years; or age \geq 13 years, weight <25 kg), or 10 mg *bid* (age \geq 13 years, weight \geq 25 kg)], or placebo *bid*.

At the start of the extension treatment period, all patients, including those previously randomized to placebo, will receive treatment with sarizotan and undergo dose titration, starting at a dose of 2 or 5 mg *bid*, dependent on age and body weight (see [Section 10.2](#)). The dose will be maintained at 2 mg *bid*, increased to 5 mg *bid*, or increased to 10 mg *bid* after 4 weeks if there are no tolerability issues.

Data from the initial 24-week double-blind period will be used for comparing the efficacy and safety of low dose sarizotan (2 and 5 mg *bid*) and high dose sarizotan (5 and 10 mg *bid*) vs. placebo. The data from the open-label extension period, during which all patients will receive sarizotan, will be analyzed separately to evaluate long-term effects of treatment. The Week 24 efficacy and safety assessments will serve as the baseline assessments for the extension treatment period.

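### With Week 24 as the only stated extension baseline, comparing placebo switchers with patients on sarizotan throughout would favour the switchers if the drug works

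*Protocol*

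**What the plan says.** Protocol 15.2.6 sets two efficacy tasks for the 168-week extension. The first is within patients randomized to sarizotan: to "determine if there is any attenuation of the benefit noted during the first six months". The second is between groups: "The response in placebo patients switched to sarizotan in the extension period will be compared with that in patients" who took sarizotan throughout. The Synopsis and 12.2.1 repeat this comparison. None of these places defines response, its scale or its reference point. Extension respiratory data come from the in-clinic SOMNOtouch.

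On the reference point, 7.3 says that "the Week 24 evaluations will be used as the baseline assessments for evaluating changes in the safety and efficacy parameters measured in the extension period", and 15.2 says: "The Week 24 efficacy and safety assessments will serve as the baseline assessments for the extension treatment period". For the global ratings, footnote K to Tables 6B-6E in 11.3 reads: "Ratings of the CGI-C and CIC for the open-label extension period should be based on the patient's condition at the Week 24 visit". Sections 12.2.2 and 12.2.3 agree.

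The method is deferred: per 15.2.6, the methodology for the "open-label extension treatment period will be described in detail in the Statistical Analysis Plan". The SAP provided (sections 1 and 4) covers only the double-blind period and points to a separate open-label SAP.

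Day 0 values do exist. For SOMNOtouch, 12.2.1 says: "Additional assessments of the respiratory outcomes will be performed at the hospital at Baseline and at the Week 16 and 24 visits". Table 6A and 11.4.2 also schedule the Motor-Behavioral Assessment Scale (MBAS), Top 3 Concerns and RCSS at Baseline.

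**The concern.** Randomization balances the arms at Day 0, not at Week 24. By Week 24 the sarizotan arms have had 24 weeks of treatment and the placebo arm has had none. Change from Week 24 therefore measures onset of effect in switchers and maintenance of effect in continuers. A benefit that is fully kept scores as no change.

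The distortion equals the drug effect already inside the continuers' Week 24 value. It is zero if sarizotan does nothing and grows as sarizotan works better. A reader of the extension report could then take a maintained benefit for a weak long-term response, or conclude that a later start does better.

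**Working it through.** **Inputs.** Protocol 15.2.8 assumes mean reductions in apnea episodes at Week 24 of 30% (high dose) against 10% (placebo), with SD 20, or 20% against 10%, with SD 12.5. The documents give no effect size or sample size for the extension comparison.

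**The plan's own figure.** Two-group t-test, two-sided 0.05, df = 2n - 2, noncentrality (difference/SD) x sqrt(n/2), smallest n with at least 90% power:
- 10/12.5 = 0.80 gives n = 34 (power 0.9015); the plan states 34.
- 20/20 = 1.00 gives n = 23 (power 0.9125); the plan states 23.

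Both reproduce, so the assumptions are read correctly.

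**Change from Week 24 and from Day 0.** Set the Day 0 mean level to 100. Change from Week 24 = (later level / Week 24 level) - 1. Assume continuers hold their Week 24 level. Full catch-up means switchers reach the continuers' level; half catch-up means they close half the distance. The calculation uses group mean levels, and the percentages do not depend on the actual episode rate at Day 0.

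| Reductions (high dose/placebo) | Catch-up | Continuers, Week 24 to later | Switchers, Week 24 to later | From Week 24: continuers / switchers | From Day 0: continuers / switchers |
|---|---|---|---|---|---|
| 20%/10% | full | 80 to 80 | 90 to 80 | 0% / -11.1% | -20% / -20% |
| 30%/10% | full | 70 to 70 | 90 to 70 | 0% / -22.2% | -30% / -30% |
| 10%/10% (no effect) | any | 90 to 90 | 90 to 90 | 0% / 0% | -10% / -10% |
| 20%/10% | half | 80 to 80 | 90 to 85 | 0% / -5.6% | -20% / -15% |
| 30%/10% | half | 70 to 70 | 90 to 80 | 0% / -11.1% | -30% / -20% |

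For example, 80/90 - 1 = -11.1% and 70/90 - 1 = -22.2%. With full catch-up, change from Week 24 shows a difference where status is equal. With half catch-up it ranks switchers ahead although their level is worse (85 against 80, or 80 against 70).

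**Including the low-dose arm among continuers.** Assume equal numbers of low- and high-dose continuers, and that low-dose patients later reach the full effect. Let the low dose have a share s of the high-dose effect at Week 24.
- 30%/10%: for s = 0, 0.5 and 1, the low-dose Week 24 level is 90, 80 and 70, and the low-dose change is -22.2%, -12.5% and 0%. Averaged with 0% for the high dose, continuers show -11.1%, -6.3% and 0%, against -22.2% for switchers.
- 20%/10%: by the same steps, continuers show -5.6%, -2.9% and 0%, against -11.1% for switchers.

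The gap shrinks to half at most in these cases and does not change direction.

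**The attenuation question.** If high-dose patients lose a quarter of the effect, the level goes from 70 to 75 (30%/10%) or from 80 to 82.5 (20%/10%). Change from Week 24 is 75/70 - 1 = +7.1% or 82.5/80 - 1 = +3.1%. The Week 24 baseline shows this loss in the right direction.

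**The case against.** The strongest reply is that the documents do not specify the analysis being criticised. Response is undefined, the method is deferred, and no sentence says that the between-arm comparison uses change from Week 24. That is correct, and the point must stay conditional. But 7.3 and 15.2 state the Week 24 rule for extension efficacy without exception, so an open-label SAP that follows the protocol has no other baseline to use. For CIC and CGI-C the issue is not only one of analysis: after Week 24 no rating against Day 0 is made.

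Second, 7.3 gives a reason for re-baselining: patients may be receiving sarizotan for the first time or at a different dose. All patients restart at Week 24 on an age- and weight-dependent dose, so continuers are not on unchanged treatment and their 0% is an assumption. This supports Week 24 for describing each group, but not for contrasting the groups. A loss of effect in continuers after restarting would widen the apparent advantage of switchers.

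Third, the effect assumptions belong to the home BioRadio endpoint, while extension apnea comes from about one hour of SOMNOtouch in the clinic. The percentages are an illustration carried over to another measure.

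Fourth, no hypothesis test or success criterion is attached to this comparison. That limits what is at stake but does not make the contrast interpretable.

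A reader might also infer that the comparison must give the wrong sign, or that the extension cannot show whether benefit is kept. The documents support neither. The ranking reverses only with partial catch-up; with full catch-up the result is a spurious difference. Attenuation within the sarizotan arms can be read from Week 24.

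**Conclusion.** The point holds in conditional form. If the protocol's stated Week 24 baseline is applied to the switch comparison, switchers gain a spurious advantage when sarizotan works, and none when it does not. Under the plan's high-dose assumptions, with effect maintained and full catch-up, this is 11.1 or 22.2 percentage points at equal true status. With low-dose patients included among the continuers in equal numbers it is between about half and all of that: 5.6 to 11.1, or 11.1 to 22.2 points. The catch-up fractions, the low-dose share and the transfer from BioRadio to SOMNOtouch are assumptions.

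The within-arm attenuation analysis is unaffected. So are the double-blind primary analysis and the win criteria, which use only data from the first 24 weeks.

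**What to change.** In Protocol 15.2 and 15.2.6 and in the open-label SAP, state the following:
- The extension comparison between randomized arms uses observed levels and change from the Day 0 baseline: SOMNOtouch at each extension visit; MBAS, Top 3 Concerns and RCSS at Week 48 and later visits where they are collected.
- Results are reported by randomized arm (low dose, high dose, placebo), so that low-dose patients are not hidden in a pooled continuing group.
- Change from Week 24 is kept for within-group description and for the attenuation analysis.
- Extension CIC and CGI-C ratings are presented within group only, because their anchor state differs by arm.

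The cost is wording; no new data are needed and the open-label SAP is still to be written. There are two downsides. CIC and CGI-C drop out of the between-arm extension comparison. The Day 0 SOMNOtouch recording lasts only about 1 hour, so change from Day 0 will be noisy, and levels should be shown beside it. Day 0 anchoring removes the baseline artefact but not selection into the extension, which under 9.2.7 takes only patients who complete Week 24 and meet the entry conditions; the report should say so.

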15.2.7 Interim analysis

There will be no interim analysis in this study.

15.2.8 Sample size and power considerations

A minimum of 129 patients with RTT will be included in this study, with approximately equal numbers of patients randomly assigned to each of the following three treatment groups:

- low dose sarizotan [sarizotan 2 mg *bid* (age 4 to <13 years; or age \geq 13 years, weight <25 kg) or 5 mg *bid* (age \geq 13 years, weight \geq 25 kg)],
- high dose sarizotan [sarizotan 5 mg *bid* (age 4 to <13 years; or age \geq 13 years, weight <25 kg), or 10 mg *bid* (age \geq 13 years, weight \geq 25 kg)],
- or placebo *bid*.

The sample size estimate was based on the following assumptions:

- 3 treatment groups (2 active + placebo)
- Primary endpoint: Percent reduction in the number of apnea episodes (\geq 10 sec each) per hour
- H_0 : Percent reduction in apnea episodes in placebo and active groups is the same
- H_A : There is a difference in the % reduction in apnea episodes between high dose sarizotan and placebo.

The assumptions for the estimated standard deviation (SD) are based on limited data from a study by Khwaja et al. (2014), in RTT patients. There were only 5 patients with data reported for apnea index (for apnea episodes \geq 10 seconds). Pilot observational data collected using the BioRadio device in 26 patients with RTT indicated that the number of episodes of apnea may approach 60 per hour. Based on the range of 10-60 episodes per hour, ranges of 10-30, 10-45 and 10-60 apnea episodes per hour indicate SDs of 5.0, 8.75 and 12.5, respectively.

Sample sizes were computed to determine the number of patients required to detect a minimum difference in mean percent reduction of 20% (high dose sarizotan 30%, placebo 10%; see Table 8) and 10% (high dose sarizotan 20%, placebo 10%; see Table 9), based on differences between high dose sarizotan and placebo.

Table 8. Sample Size Estimates Assuming 90% Power and – 20% Difference

Parameter	1	2	3	4
Test significance level, α	0.050	0.050	0.050	0.050
1 or 2 sided test?	2	2	2	2
High Dose mean % Chg, μ_1	-30.00	- 30.00	- 30.00	-30.00
Placebo mean % Chg, μ_2	-10.00	-10.00	-10.00	-10.00
Difference, $\mu_1 - \mu_2$	-20.00	-20.00	-20.00	-20.00
Common St. Dev., σ	12.50	15.00	20.00	25.00
Effect size, $\delta = \mu_1 - \mu_2 / \sigma$	1.60	1.33	1.00	0.80
Power (%)	90	90	90	90
n per group	10	13	23	34

Table 9. Sample Size Estimates Assuming 90% Power and – 10% Difference

Parameter	1	2	3	4
Test significance level, α	0.050	0.050	0.050	0.050
1 or 2 sided test?	2	2	2	2
High Dose mean % Chg, μ_1	-20.00	- 20.00	- 20.00	-20.00
Placebo mean % Chg, μ_2	-10.00	-10.00	-10.00	-10.00
Difference, $\mu_1 - \mu_2$	-10.00	-10.00	-10.00	-10.00
Common St. Dev., σ	20.00	12.50	8.75	5.00
Effect size, $\delta = \mu_1 - \mu_2 / \sigma$	0.50	0.80	1.14	2.00
Power (%)	90	90	90	90
n per group	86	34	18	7

Sample sizes of 23 or 34 in each treatment group will have 90% power to detect a difference in mean percent reduction of -20% or -10%, respectively, assuming a common SD of 20 (for the 20% reduction) and 12.5 (for the 10% reduction), using a two group t-test with a 0.050 two-sided significance level. Assuming an attrition rate of 25% (7 or 9 patients) per group, a total of 30 or 43 patients would need to be enrolled in each group to get 23 or 34 patients completing the study. As this is the first large-scale study evaluating the effect of sarizotan on respiratory symptoms in patients with RTT, a conservative estimate of 10% reduction in apnea episodes was used to estimate the sample size required, i.e. approximately 43 patients per group. The sample size may be revised based on a prospective assessment of variability in the frequency of apnea episodes of 10 seconds or greater duration, from data collected from the first 20 patients who complete screening.

Details of all statistical analyses will be provided in a separate Statistical Analysis Plan, which will be completed prior to unblinding of the data at the Week 24 endpoint.

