A randomized, double-blind study design will be used for the initial 24-week treatment period of this study to reduce potential bias in the assignment of patients to treatment and in the assessment of efficacy and safety parameters. A total of 129 patients will be included in this study, with approximately equal numbers of patients randomly assigned (1:1:1) to treatment with low dose sarizotan [2 mg *bid* (age 4 to <13 years; or age ≥13 years, weight <25 kg) or 5 mg *bid* (age ≥13 years, weight ≥25 kg)], high dose sarizotan [5 mg *bid* (age 4 to <13 years; or age ≥13 years, weight <25 kg), or 10 mg *bid* (age ≥13 years, weight ≥25 kg)], or placebo *bid*. The approximately equal randomization to each group allows for a drug-placebo comparison for safety and efficacy for each dose. Samples sizes were computed based on percent reductions of 20% and 10% between the sarizotan high dose and placebo groups, assuming an attrition rate of 25%, and a SD of 20 or 12.5, respectively. The sample sizes of 30 or 43 per group provides 90% power to detect a difference of -20% (-30% for sarizotan high dose vs. -10% for placebo) or -10% (-20% for sarizotan high dose vs. -10% for placebo) in the percent reduction in apnea episodes per hour (apnea index).

There are currently no approved treatments for respiratory abnormalities in RTT patients; therefore, a placebo control, rather than an active control, will be used in this study. The use of a device to record respiration as well as the structured method of observation may lead to learning effects. The placebo control has been included so that a background rate of spontaneous occurrence of adverse events, as well as changes in other safety and efficacy parameters, can be established in placebo-treated patients, against which the active treatment will be compared, without introducing a bias from knowledge of the treatment by the caregivers or investigators.

Amend. 1, 19Jan2016; Amend. 2, 18May2016; Amend. 3, 21Oct2016; Amend. 4, 03Mar2017; Amend. 5, 29Mar2017; Amend. 6, 13Apr2017; Amend. 7, 02Oct2017; Amend. 8, 02Nov2017; Amend. 9, 11Feb2018; Amend. 10, 29Nov2018; Amend. 13, 10Dec2019; Amendment 14, 17 March 2020, Clean, Final

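### At 25% attrition, 43 per group leaves about 32 completers and about 88% power on the plan's own t-test basis, not 34 completers and 90%

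*Protocol*

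**What the plan says.** Protocol 15.2.8 works through two scenarios for high dose against placebo. The one that matters here is a difference of "10% (high dose sarizotan 20%, placebo 10%; see Table 9"), with a common SD of 12.5, "using a two group t-test with a 0.050 two-sided significance level". Before dropout it states: "Sample sizes of 23 or 34 in each treatment group will have 90% power to detect a difference in mean percent reduction".

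The dropout step then reads "Assuming an attrition rate of 25% (7 or 9 patients) per group, a total of 30 or 43 patients would need to be enrolled". That enrolment is meant to leave 23 or 34 completers per group. The section chooses between the scenarios by saying that "a conservative estimate of 10% reduction in apnea episodes was used to estimate the sample size required, i.e. approximately 43 patients per group". Three groups of 43 give the stated minimum of 129. The Synopsis and SAP 3.1 carry the same attrition sentence and the same counts.

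Protocol 7.3 summarises the calculation without naming a number of completers. It says that sizes were computed "assuming an attrition rate of 25%, and a SD of 20 or 12.5, respectively", and then: "The sample sizes of 30 or 43 per group provides 90% power" for the two differences.

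**The concern.** The sentence ties together a rate (25%), a loss (9), an enrolment (43) and a number of completers (34). The counts agree with each other, since 43 − 9 = 34, but the rate does not agree with them. Protocol 7.3 drops the counts and keeps the rate, so the mismatch there becomes a power claim for 43 per group at 25% dropout.

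What is at stake is how much dropout the design can absorb. A reader would conclude that the trial keeps 90% power while losing a quarter of each group. On the plan's own calculation, 43 per group holds 90% only up to about one fifth lost.

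**Working it through.** **Inputs (Protocol 15.2.8, Tables 8 and 9)**

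- Test: two-group t-test, two-sided α = 0.05, equal group sizes.
- 10-point scenario: Δ = 10, σ = 12.5, so δ = 10/12.5 = 0.80.
- 20-point scenario: Δ = 20, σ = 20, so δ = 1.00.
- Attrition 25%; enrolled 43 or 30; stated completers 34 or 23.

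**Step 1. Reproduce the plan's figure before dropout.** Power comes from the noncentral t distribution with df = 2n − 2 and noncentrality λ = δ√(n/2). The smallest n with at least 90% power at δ = 0.80 is 34 (λ = 0.80 × √17 = 3.30, power 90.15%). This matches Table 9, and all eight group sizes in Tables 8 and 9 reproduce in the same way. The requirement of 34 completers is correct.

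**Step 2. Check the attrition step.** Completers = enrolled × (1 − attrition).

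- 25% of 43 = 10.75, so 43 × 0.75 = 32.25 completers.
- The stated loss of 9 is 9/43 = 20.9%.
- Shortfall against 34: 34 − 32.25 = 1.75 completers per group.

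**Step 3. Where 43 probably came from.** 34 × 1.25 = 42.5, which rounds up to 43. That adds 25% of the completers, whereas attrition is a loss among those enrolled. Dividing by the retained fraction gives 34/0.75 = 45.3, so 46. This explanation is offered for 43 only: 23 × 1.25 = 28.75 does not give the 30 used in the other scenario.

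**Step 4. Power in the 10-point scenario (t-test on completers)**

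| Enrolled per group | Attrition | Completers | Power |
|---|---|---|---|
| 43 | 20.9% | 34 | 90.2% |
| 43 | 25% | 32.25 | 88.5% |
| 43 | 25%, rounded down | 32 | 88.3% |
| 45 | 25% | 33.75 | 89.9% |
| 46 | 25% | 34.5 | 90.6% |

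The loss against 34 completers is 1.6 to 1.9 points. Holding both 25% and 34 completers needs 46 per group, and 3 × 46 = 138 against 129.

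**Step 5. The 20-point scenario.** 7/30 = 23.3%, and 30 × 0.75 = 22.5. Power is 91.2% at 23 completers, 90.6% at 22.5 and 89.97% at 22. Only the percentage label is loose, and this scenario did not set the trial size.

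**The case against.** The strongest reply is that the primary analysis is not a t-test on completers. Protocol 15.2.6 and SAP 15.1.3 specify an MMRM on all randomized patients with data from Weeks 2, 8, 16 and 24, so a patient who leaves early still contributes. Protocol 7.3 mentions neither a t-test nor completers.

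The documents give no within-patient correlation and no dropout timing, so the gain can only be illustrated on assumptions. Take 43 per group, 25% lost by Week 24, data missing at random and no gain from covariates. If the losses fall evenly after Weeks 2, 8 and 16, the Week 24 contrast has about 88.9% to 93.7% power for assumed correlations of 0.3 to 0.8. If every dropout leaves before any post-baseline recording, it has 88.5%. The MMRM may therefore reach 90% or may not. This part of the objection stands as a limit: 88% is the completer t-test figure and not the power of the planned analysis. It does not rescue the text, because the only power calculation in the documents is the t-test, and Protocol 7.3 repeats its differences, SDs, attrition rate and group sizes.

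It can also be said that 43 is approximate, that 129 is a minimum, and that the effect is small beside the uncertainty in the SD: across the SDs in Table 9 the group size runs from 7 to 86. All of that is true and argues for a low rating. It does not make 9 of 43 equal to 25%.

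**Conclusion.** The concern holds and is minor. For 43 per group, 25% attrition and 34 completers cannot both be true, and 90% power at 25% attrition does not follow from the plan's stated calculation. On that basis the design gives about 32 completers and about 88% power, or 90% power with attrition up to about 21%.

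This rests on the plan's own difference of 10 points, SD of 12.5, two-sided 0.05 level and t-test on completers, with 25% read as a share of those enrolled. The statement that 34 completers give 90% power is correct. The 20-point scenario keeps about 90% either way.

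**What to change.** Make the figures consistent in the Synopsis (Sample Size), Protocol 7.3, Protocol 15.2.8 and SAP 3.1. Either wording below removes the contradiction:

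- **Preferred, because it keeps the stated attrition assumption:** *Assuming attrition of 25%, 43 patients per group gives about 32 completers and about 88% power (two-group t-test on completers).*
- **Alternative:** *43 patients per group gives 34 completers and 90% power (two-group t-test on completers) if attrition is no more than about 21% (9 of 43).*

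For 30 per group a small correction to the label is enough: 7 of 30 is 23%, or about 22 completers at 25%, with power still about 90%.

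With either wording the minimum of 129 stands and no analysis changes. The cost is a text edit and a slightly less favourable statement of power or of the dropout covered. Only a decision to keep both 25% attrition and 34 completers would add patients: 46 per group, 9 more in total (138 against 129).
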